#### 9.5 Integrated Pharmacodynamic Biomarker Study of Acute Change in Protein Lysine Acetylation

HDAC inhibition leads to elevated protein lysine acetylation in tumor and peripheral-blood cells, which could serve as a surrogate early pharmacodynamic biomarker of entinostat activity. ENCORE 301 collected peripheral blood samples (PBMCs) for assessment of lysine acetylation, both prior to therapy and post-therapy on Days 8 and 15, using an assay developed by the [name] Laboratory, NCI/NIH. Protein lysine acetylation in the combined therapy subgroup (i.e., arm A) was associated with a striking improvement in PFS across all cell types (B cells, T cells and monocytes). In Exemestane +Entinostat-treated hyperacetylators (i.e., acetylatoin above the median) versus those with acetylation below the median, median PFS was 8.5 versus 2.7 months (HR=0.32, 95% CI 0.13, 0.79) (B cells); 6.6 versus 3.6 months (HR=0.44, 95% CI 0.18, 1.08) (T cells); and 6.2 versus 3.6 months (HR=0.50, 95% CI 0.21, 1.20) (monocytes).

We will use the identical methodology, central laboratory ([name] Laboratory, NCI/NIH), and timing (Day 15) for the integrated acetylation pharmacodynamic

Rev. 9/17

biomarker studies planned in E2112. PBMCs will be collected at baseline and 15 days after initiating therapy consisting of drawing 8cc of blood into one blue/black CPT citrate tube at each time point.

Since exemestane is not expected to induce significant increase in protein lysine acetylation, we expect no significant increase in protein lysine acetylation after two weeks of arm B treatment on E2112. The primary test of association between increased protein lysine acetylation (as an early pharmacodynamic biomarker of entinostat activity) and PFS will be examined in arm A in E2112. However, since the study is blinded, the PBMCs will be collected on all patients (including both arm A and arm B). The prognostic value of increase of lysine acetylation will be conducted in arm B as well as an exploratory analysis. All 600 patients enrolled in the main trial will be included in the integrated acetylation pharmacodynamic biomarker study. The analysis will be performed at about 70 months after study activation (same time as that for final OS analysis).

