#### 9.5.1 Statistical consideration for integrated acetylation pharmacodynamic biomarker study

The objective of this pharmacodynamic biomarker study is to examine the prognostic value of acute acetylation change for PFS in patients receiving Exemestane + Entinostat combination therapy. We hypothesize that patients with percentage change in protein lysine acetylation above median will have a prolonged PFS compared to those with changes in protein lysine acetylation below or equal to median in arm A. For this integrated pharmacodynamic biomarker study, the endpoint is PFS. The group variable is change in protein lysine acetylation between baseline and 2 weeks after initiating therapy.

Of the 300 refractory patients on arm A, 270 (90%) of them will be expected to have measures for protein lysine acetylation at both baseline and 2 weeks after initiating therapy. The percentage change in lysine acetylation will be calculated for all patients on arm A and the median percentage change will be determined and used as the threshold to dichotomize all patients into two groups on the arm:  $>$  median and  $\leq$  median. There will be about 266 PFS events on arm A at the time of the analysis (70 months after study activation) under the alternative hypothesis. With a total of 266 PFS events and 270 patients, there will be adequate power (80%) to detect a hazard ratio of 0.71 and excellent power (90%) to detect a hazard ratio of 0.67 using log rank test with one-sided type I error equal to 2.5%.

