All above analyses for protein lysine acetylation change will be repeated for all three types of peripheral blood mononuclear cells (CD3+ T cells, CD19+ B cells and CD14+ monocytes). In all analyses, P-values will be two-sided and a level of 5% will be considered statistically significant. No adjustment will be made for multiple comparisons.

If PFS endpoint is positive in the primary analysis within the first 360 patients, the acetylation data will be analyzed for a subgroup analysis for PFS (all 360 patients will be dichotomized into one of two groups based on the whole sample median: > median and ≤ median) at the PFS primary analysis time.

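### The acetylation biomarker study powers one primary test but runs it in three blood-cell types without naming a primary one, so its stated error and power attach to no single result

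*Combined protocol and SAP*

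**What the plan says.** Section 9.5 describes a single primary test, in arm A, of increased acetylation against PFS, and labels the arm B version exploratory. Section 9.5.1 splits the arm A patients at the median: "the median percentage change will be determined and used as the threshold to dichotomize all patients into two groups on the arm". It powers one comparison: "With a total of 266 PFS events and 270 patients, there will be adequate power (80%) to detect a hazard ratio of 0.71", with 90% power at 0.67, both at one-sided 2.5%.

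Section 9.5.2 then says: "All above analyses for protein lysine acetylation change will be repeated for all three types of peripheral blood mononuclear cells", and lists CD3+ T cells, CD19+ B cells and CD14+ monocytes. The level is set per test: "In all analyses, P-values will be two-sided and a level of 5% will be considered statistically significant". The next sentence reads: "No adjustment will be made for multiple comparisons".

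Neither Section 9.5 nor Section 12.1 ranks the three cell types, combines them, or says how many must be positive. The question is a listed secondary objective (2.2.3), not one of the exploratory objectives in 2.3.

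**The concern.** A test that is called primary and given its own power calculation has to be identifiable before the data are seen. Here three versions qualify equally. If one is positive and two are not, the plan does not say whether the primary hypothesis has been supported.

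The phase 2 results in Section 9.5 show how this could arise. The hazard ratios were 0.32 (95% CI 0.13 to 0.79) for B cells, 0.44 (0.18 to 1.08) for T cells and 0.50 (0.21 to 1.20) for monocytes, so only one interval excluded 1. Section 1.3.4 summarises the same data as a median PFS of 8.5 months in hyperacetylators and names no cell type. Section 9.5 shows that 8.5 months is the B-cell figure, the largest of 8.5, 6.6 and 6.2. As written, Section 9.5.2 leaves room for the same kind of summary in this trial.

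What is at stake is how a secondary biomarker finding is read. The primary efficacy conclusions are not involved.

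**Working it through.** **Inputs from the documents.** 266 PFS events in arm A, a median split (so 50:50), one-sided 2.5% and hazard ratios 0.71 and 0.67 (9.5.1); three cell types, two-sided 5% per test and no adjustment (9.5.2).

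**Input not in the documents.** The correlation between acetylation changes in the three cell types. I assume equal pairwise correlation ρ and bivariate normality, and show a range.

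**Step 1: reproduce the stated power.** For one log-rank test with equal groups, power = Φ(√(events/4) × |ln HR| − z), with √(266/4) = 8.155 and z = 1.960.
- HR 0.71: 8.155 × 0.3425 = 2.793; Φ(2.793 − 1.960) = 79.8%.
- HR 0.67: 8.155 × 0.4005 = 3.266; Φ(3.266 − 1.960) = 90.4%.

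Both agree with the plan, so its figures are those of a single test.

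**Step 2: at least one false positive among three tests, independent case.**
- Hypothesised direction only: 1 − 0.975³ = 7.3%.
- Two-sided: 1 − 0.95³ = 14.3%.

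**Step 3: allow for correlation.** With no association, the correlation between two log-rank statistics from median splits is (2/π) × arcsin ρ, which is smaller than ρ. Numerical integration over three equicorrelated normal statistics gives:

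| Marker correlation ρ | Test correlation | Hypothesised direction (2.5% for one test) | Two-sided (5% for one test) |
|---|---|---|---|
| 0 | 0 | 7.3% | 14.3% |
| 0.3 | 0.19 | 7.0% | 14.0% |
| 0.5 | 0.33 | 6.8% | 13.5% |
| 0.7 | 0.49 | 6.3% | 12.6% |
| 0.9 | 0.71 | 5.4% | 10.8% |
| 0.95 | 0.80 | 4.9% | 9.8% |
| 1 | 1 | 2.5% | 5.0% |

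The nominal level is recovered only when the three tests are identical.

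**Step 4: cost of the two remedies.**
- One primary marker: Step 1 applies unchanged.
- Three primary markers at the Bonferroni level, which is the first step of Holm: one-sided 0.025/3 = 0.00833, z = 2.394. Power at HR 0.71 is Φ(2.793 − 2.394) = 65.5%; at HR 0.67 it is Φ(3.266 − 2.394) = 80.8%. The hazard ratio detectable with 80% power is exp(−(2.394 + 0.842) × 2/√266) = 0.67, and with 90% power exp(−(2.394 + 1.282) × 2/√266) = 0.64.

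**The case against.** The best defence is that nothing is hidden. The 5% in 9.5.2 is a per-test level and the next sentence disclaims adjustment. A reader might infer that the plan claims 5% overall while the true figure is 11% to 14%. The documents do not support that, because 9.5.2 makes no familywise claim. The two-sided figures also count results in which hyperacetylators do worse. The hypothesis in 9.5.1 is directional, so the matching comparison is 5.4% to 7.3% against 2.5%.

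A reader might also infer that the trial fails in a duty to confirm the phase 2 B-cell signal. Section 12.1 says these data will not contribute independently to validation, and Section 1.4 places validation of the marker in a separate planned phase II study. Nor is there a written rule that one positive cell type is enough. It would also go too far to say that acetylation is never measured as one quantity: Section 12.1 refers to global protein acetylation in PBMCs, although no pooled measure is defined for the test.

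Finally, all three samples come from the same tube and assay, so the correlation could be high. That is possible, but nothing in the documents fixes it. Even at 0.9 the directional figure is about twice the nominal level.

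These points limit the concern to its proper size. They do not remove it. Leaving supportive tests unadjusted is reasonable once a primary test has been named, and here none has. The neighbouring PRO analysis (9.6 and 9.6.1), also secondary, divides its error between two objectives and then across four symptoms (0.025/4 = 0.00625).

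**Conclusion.** The point holds as a gap in specification. One primary test is described and powered, three unranked versions will be run, and the stated 2.5% and 80% cannot be assigned to any of them. Under the correlation and normality assumptions above (marker correlation 0 to 0.9), the chance of at least one false positive in the hypothesised direction is about 5.4% to 7.3%, against 2.5%. The logical limits are 2.5% (identical tests) and 7.3% (independent tests). The count covers only the three arm A PFS tests, and leaves out the OS, response, Cox and arm B analyses.

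This affects secondary objective 2.2.3 alone. The 0.001 and 0.024 allocated to PFS and OS in Section 9.1 are unaffected. The change is worth making, but the validity of the trial does not depend on it.

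**What to change.** Before acetylation data are linked to outcome, designate one primary acetylation measure in 9.5.1 and 9.5.2, test it at two-sided 5%, and describe the other cell types as supportive. CD19+ B cells are a reasonable candidate, as the only cell type whose phase 2 interval excluded 1. That is a weak ground for preferring them: the phase 2 acetylation subset had 27 patients (1.3.4), and all three hazard ratios pointed the same way with overlapping intervals. The choice is the sponsor's. If a pooled PBMC measure is intended, it should be defined and designated instead. The same designation should govern the acetylation subgroup analysis that 9.5.2 triggers in the first 360 patients if PFS is positive, which also names no cell type.

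This takes about two sentences and no extra patients, and it keeps the stated error and power. The downside is that a positive result confined to a non-primary cell type becomes supportive only.

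The alternative is to keep all three as primary under Holm and restate the hazard ratio detectable with 80% power as about 0.67 in place of 0.71. Power for a given cell type at 0.71 would be about 65.5% at the Bonferroni level.

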## 9.6 Patient-Reported Outcomes Assessment

There are two objectives in the patient-reported outcomes (PROs) assessment study. The first objective is to compare overall HRQL between treatment arms. The second objective is to compare symptoms associated with entinostat between arms. The type I error rate is equally split between the two objectives to control the overall one-sided type I error at 2.5% for the PROs analysis. In order to provide sufficient power for the two objectives, all 360 patients included for the PFS endpoint on the main study and receive at least one dose of protocol therapy (i.e., all treated patients) will be eligible for the PROs study. PROs will

not be evaluated on the additional 240 patients primarily enrolled for the OS endpoint.

Rev. Add7

With the exception of the FBSI and the Medication Adherence Scale, the PROs assessment will be administered at the following time points: baseline, 3, 6, and 12 months (the timing of these assessments coincides with the first, second and fourth disease assessments), at the end of protocol treatment/time of protocol treatment discontinuation and 4 weeks after protocol treatment is discontinued. Given that anticipated median survival is about 2 years and median PFS is about 4-7 months, the 3-month assessment is expected to provide the best assessment of treatment-emergent symptoms. Hence the primary comparison of PROs between treatment arms is based on the month 3 assessment.

#### 9.6.1 Statistical consideration for PROs

The primary objective of the PROs study is to test whether the overall HRQL is significantly worse in the Exemestane + Entinostat arm (arm A) compared to the Exemestane + Placebo arm (arm B) at month 3. The null hypothesis is that patients on the two arms have same overall HRQL. The alternative hypothesis is that patients on arm A have worse HRQL than patients on arm B. The endpoint for the objective is the overall HRQL score measured by the Trial Outcome Index (TOI), an aggregate score of the 5 items from the FACT-G-Physical subscale (GP2, GP3, GP4, GP6, and GP7), and 6 items from the FACT-G-Functional subscale (GF1, GF2, GF3, GF4, GF6, and GF7). Higher score represents better HRQL (score range 0-44).

Assuming an overall attrition rate of approximately 10% by month 3 for the PROs assessment in both arms, it is expected that about 324 refractory patients will be included for the primary analysis for HRQL. At month 3, a difference of 5 points in the overall HRQL score between the treatment arms would be considered clinically meaningful. The common standard deviation is expected to be 12 points. With 162 analyzable patients on each arm for the month 3 assessment, there will be about 93% power to test the difference using a two independent samples t test, assuming a two-sided type I error of 0.025.

The second objective of the PROs study is to assess differences between the two arms in symptoms associated with entinostat at month 3 (i.e., fatigue, nausea, anorexia and diarrhea, measured by PROMIS Fatigue short form, FAACT-additional concerns and FACIT-Diarrhea, respectively). The null hypothesis is that there is no difference between two arms regarding fatigue, nausea, anorexia and diarrhea at 3-month assessment. The alternative hypothesis is that patients on the Exemestane + Entinostat arm have more severe symptoms than patients on the Exemestane + Placebo arm. For each of the four symptoms, with 162 analyzable patients on each arm in the study, there will be an adequate power (80%) to detect an effect size of 0.40 and an excellent power (90%) to detect an effect size of 0.45, using two independent samples t test, assuming a two-sided type I error of 0.00625 (=0.025/4). The effect size is the difference in the survey score between two arms divided by the population standard deviation for each symptom.

For the fatigue assessment, the clinically minimally important differences (MIDs) have been estimated for the PROMIS Fatigue short form in advanced-stage cancer patients, which is 3.0-5.0 points and corresponds to effect sizes between 0.4 and 0.63. For the nausea/anorexia assessment, the clinically minimally important difference is estimated to be 6 points using the FAACT-additional concerns subscale, corresponding to an effect size of 0.53. For the diarrhea assessment, we are planning to use the FACIT-Diarrhea subscale, which does not yet have published MIDs. We propose using 1/2 of the standard deviation of the FACIT-D scores (this is comparable to an effect size of 0.5) along with a general estimate of 0.36 points per item. Since the FACIT-D has 11 items, the estimated MID would be 4 points. Overall, this study should have an at least adequate power to detect a clinically important difference in each of the four symptoms, controlling the overall type I error rate at 2.5% for the second objective.

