PRO assessments at treatment discontinuation and 4 weeks post-treatment discontinuation for all participants regardless of the reason for treatment discontinuation (toxicity, progression) will provide valuable information on HRQL and symptom burden. As noted by Rini et al. HRQL can appear to improve overall as the trial progresses due to participant selection bias. Participants with poorer performance status, more aggressive disease, and greater treatment toxicities come off treatment earlier. We may observe a high rate of attrition due to progression of illness. Patients on EE are expected to remain on treatment longer than patients on EP due to anticipated benefit in PFS. To obtain an unbiased assessment of HRQL and treatment toxicities, PRO assessment at the end of treatment and a short period of time following end of treatment (4 weeks) for all participants is needed. Otherwise, PRO assessments only capture data on participants who remain on treatment and are likely to be healthier, therefore, presenting a biased source of data that will likely indicate that HRQL improves over time. In addition, the assessment 4 weeks post-end of treatment will evaluate whether entinostat-related symptoms resolve within 4 weeks. This design (retaining participants who discontinue treatment) has been employed with other PROs studies such as the side effect sub-study of MA.27.

Rev. Add7

A PRO measure of breast cancer-specific symptoms will be administered at baseline, and every 28-day cycle for the first six months after randomization, and then every two cycles between 6 months and 1 year. After 1 year, the FBSI will be administered on the same schedule as tumor assessments until disease progression. The FBSI will be administered more frequently to allow for an assessment of time to treatment deterioration (TTD), a critical secondary endpoint.

The PRO measure of adherence to therapy, the Medication Adherence Scale - , will be administered as outlined in Section [5.6.3](#) (before Cycle 4, 7, 13, and end of protocol therapy). With the exception of baseline, these assessment time points correspond with other study PRO.

The FBSI and Medication Adherence Scale include 8 and 8 items each and the anticipated time to complete the 16 items is roughly 5-6 minutes. Please note there will be one Medication Adherence Scale form completed for each agent (entinostat/placebo and exemestane).

Rev. Add7

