### 9.2 Study Design

Patients with histologic confirmation of invasive adenocarcinoma of the breast will be randomized according to the permuted block algorithm with a 1:1 randomization ratio to arms A and B. Stratification factors include:

- Setting in which patient developed resistance to prior non steroidal AI treatment (adjuvant vs. metastatic)
- Geographic region (USA vs. other)
- Visceral disease (yes vs. no)
- Prior fulvestrant use (yes vs. no)

**NOTE:** Visceral disease is defined as lung and/or liver involvement.

Taking into consideration the accrual rates of the BOLERO-2 study (40 patients/month, 700 patients over 18 months with 24 international sites), the ENCORE 301 study (5 patients/month, 130 patients over 2 years at 38 sites US and international) and the CONFIRM study (24 patients/month at 128 sites), all of which have been conducted in the AI refractory setting, and the 1st line SWOG

S0226 study (10 patients/month, 700 patients over 6 years), we anticipate an accrual rate of approximately 15 patients per month in our study.

Enrollment of 600 patients will be required to provide adequate power for the OS endpoint (see Section [9.2.2](#)). The first 360 patients will be used for the primary evaluation of PFS (see Section [9.2.1](#)), objective response rate (ORR), toxicity, time to treatment deterioration and patient-reported outcomes. If the PFS analysis is positive, the data for first 360 patients would be used for a submission to the FDA. At the time of final analysis for the OS endpoint, secondary analyses of PFS, objective response and toxicity will be conducted in all 600 patients, along with the primary analyses for the pharmacodynamic acetylation marker data and adherence to protocol therapy data. Imaging studies for all 600 participants will be collected and archived at the ACR Imaging Core Laboratory.

For purposes of comparability to the phase 3 study of exemestane in advanced breast cancer patients by Chia et al., enrollment in this study will attempt to achieve a target patient population that consists of approximately 80% of patients having measurable disease (with at least 1 measurable lesion at baseline assessment and identification of up to 5 total target lesions [maximum of 2 lesions per organ] and 5 total non-target lesions) and approximately 20% of patients having non-measurable disease only.

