In order to fully capture the impact of toxicity and disease progression before radiological assessment on patient’s QOL, symptoms will be assessed every cycle for the first six months after randomization, every two cycles between 6 months and 1 year. It then will be assessed based on the same schedule for tumor assessments until disease progression. Since symptom change cannot be associated with protocol therapy if the patient never receives any treatment on protocol, the primary population for the TTD analysis will be the enrolled 360 patients for the PFS analysis who receive at least one dose of protocol therapy (i.e., all treated patients in the first 360 enrolled patients). TTD will not be evaluated on the additional 240 patients primarily enrolled for the OS endpoint.

Because we expect that the benefits from improving PFS (and thus less symptoms from disease) on arm A will outweigh any increase in toxicity from the addition of entinostat to exemestane (more symptoms from the treatment), we hypothesize that the combination arm (A) will have a significantly longer TTD than arm B. It is expected that symptom deterioration will occur before radiological confirmed disease progression or death for some patients. Hence, the median TTD should be shorter than the median PFS for the same patient population. To be conservative, we assume that the median TTD is 4 months for patients on arm B, similar with our estimate for PFS in these patients. Assuming 9 patients (9/180=5%) will not start protocol therapy in each arm, with 171 evaluable patients per arm, there is 88% power to detect a HR of 0.67 for arms A/B based on the log-rank test when the analysis is conducted 30 months after study activation (same time as the primary analysis of PFS), assuming a median TTD

of 6 months on arm A (i.e., 50% improvement in median TTD), with a 2.5% one-sided type I error rate.

Rev. Add5

9.4 Analysis Plan for Primary Endpoints, Objective Response, Toxicity and Time to Treatment Deterioration

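### PRO sample size takes 10% attrition from all 360 patients although only treated patients are eligible, and the primary month-3 t test is open to loss that may differ by arm

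*Combined protocol and SAP*

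**What the plan says.** Section 9.6 draws the PRO population from the first 360 patients and limits it to those treated: patients who "receive at least one dose of protocol therapy (i.e., all treated patients) will be eligible for the PROs study". The primary comparison is at month 3.

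Section 9.6.1 sets the sample size by "Assuming an overall attrition rate of approximately 10% by month 3 for the PROs assessment in both arms". From this "it is expected that about 324 refractory patients will be included for the primary analysis for HRQL", and the HRQL power is computed "With 162 analyzable patients on each arm for the month 3 assessment". The stated powers are:
- about 93% for a 5-point HRQL difference (SD 12, two-sided 0.025);
- 80% at effect size 0.40 and 90% at 0.45 for each of four symptoms (two-sided 0.00625).

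For the same treated group, Section 9.3.3 works with a smaller base: "Assuming 9 patients (9/180=5%) will not start protocol therapy in each arm, with 171 evaluable patients per arm". Section 9.3.2 does likewise for toxicity.

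Section 5.6 foresees possibly high attrition from progression and expects longer treatment on the entinostat arm. It justifies the end-of-treatment and 4-week forms by saying that without them "PRO assessments only capture data on participants who remain on treatment and are likely to be healthier". Section 9.6.2 analyses those later forms as separate time points, describes missing-data patterns, and keeps mixed models as exploratory.

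**The concern.** Two things do not fit together.

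First, the base of the calculation. Patients who never start treatment are outside the PRO study by the plan's own definition, yet 324 is 90% of a total that includes them. The 80% at effect size 0.40 has no slack, since 162 per arm is the smallest number that reaches it. That effect size is the lower end of the plan's range of minimally important differences (MIDs) for fatigue, and fatigue is the side effect that Section 1.5 expects most often.

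Second, the primary analysis. The month-3 form is an end-of-cycle-3 form. A patient who stops earlier gets an end-of-treatment form but no scheduled month-3 form, and the plan has no rule for that patient in the month-3 t test. If the placebo arm loses more patients to early progression, its remaining patients are the more selected. The test of whether entinostat worsens HRQL or symptoms then compares groups that randomization no longer balances.

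**Working it through.** **Inputs.** First 360 patients, randomized 1:1 (Section 9.2); 10% attrition, HRQL difference 5, SD 12, effect sizes and alphas (Section 9.6.1); 9 non-starters per arm (Section 9.3.3); exponential PFS with medians of 7.1 months on arm A and 4.1 on arm B (Section 9.2.1).

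**Formula.** Two-sample t test: noncentrality = d / √(1/n_A + 1/n_B), critical value t at 1 − α/2 on n_A + n_B − 2 degrees of freedom, power from the noncentral t distribution.

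**Step 1: reproduce the plan.** 360 × 0.90 = 324, or 162 per arm, and √(162/2) = 9.
- HRQL: d = 5/12 = 0.4167, noncentrality 3.75, critical value 2.252, power 93.2%.
- Symptoms at 0.40: noncentrality 3.60, critical value 2.752, power 80.1%.
- Symptoms at 0.45: noncentrality 4.05, power 90.2%.

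All three stated powers reproduce at 162 per arm.

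**Step 2: take 10% from treated patients.** 2 × 171 = 342; 342 × 0.90 = 307.8, about 154 per arm; √(154/2) = 8.775.

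| Comparison | Stated | 162 per arm | 154 per arm |
|---|---|---|---|
| HRQL, 5 points | about 93% | 93.2% | 91.9% |
| Symptom, 0.40 | 80% | 80.1% | 77.5% |
| Symptom, 0.45 | 90% | 90.2% | 88.3% |
| Symptom, 0.50 (diarrhea MID) | – | 95.9% | 94.8% |
| Symptom, 0.53 (nausea/anorexia MID) | – | 97.8% | 97.1% |

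**Step 3: the other reading.** If the 10% already contains the non-starters, the loss left for treated patients is (171 − 162)/171 = 5.3%.

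**Step 4: how large might early loss be?** The documents give no rate of leaving treatment before the form is due. As an illustration only, take the exponential medians at 12 weeks (84 days, 2.76 months). The proportion progression-free is 0.5^(2.76/7.1) = 76% on arm A and 0.5^(2.76/4.1) = 63% on arm B. Applied to 171 per arm, with the missing-form rates below assumed:

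| Assumption | n, A vs B | HRQL | Symptom 0.40 |
|---|---|---|---|
| Half of progressors miss the form, 5% other loss | 143 vs 132 | 88% | 71% |
| All progressors miss it, no other loss | 131 vs 107 | 83% | 62% |
| All progressors miss it, 5% other loss | 124 vs 102 | 80% | 59% |

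First row, arm A: 171 × 0.95 × (1 − 0.5 × 0.236) = 143. Arm B: 171 × 0.95 × (1 − 0.5 × 0.373) = 132. In that row, power is still 91.6% at 0.50 and 94.8% at 0.53. The difference between arms presumes that the alternative hazard ratio of 0.58 is true.

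**The case against.** The strongest reply is that no arithmetic error is shown. The attrition is called overall, which can include patients who never start; 360 × 0.9 is correctly 324, and every stated power reproduces. This stands as a possible reading, and the documents do not settle it. A reader might infer that the stated 80% is simply not delivered; that holds only if the 10% is additional to non-starters. The benign reading has its own cost, though: a 5.3% loss among treated patients sits poorly with the warning in Section 5.6.

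The second reply is that the effect is small. This also stands. HRQL loses about one point, and only the power at 0.40 moves by more than two. The plan's claim of adequate power survives at the diarrhea and nausea/anorexia MIDs.

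The third reply concerns drop-out. A reader might infer from the PFS medians that many patients leave treatment before month 3 and that symptom power falls to 60–70%. The documents do not support that as a finding. The first scheduled scan is at 12 weeks, when the form is also due, so many progressors may still complete it, and Section 5.6.4 provides mail and telephone back-up. The Step 4 scenarios are assumptions and do not strictly bound the range.

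Finally, a reader might infer that the plan calls its own month-3 comparison biased. It does not: the Section 5.6 sentence describes what would happen without the off-treatment forms, which are scheduled and compared between arms. What remains is that those forms do not enter the primary month-3 test.

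**Conclusion.** The point holds in a limited form. The count of 324 rests on all 360 patients, while eligibility rests on treated patients, whom the plan elsewhere puts at 342. On the additional-loss reading, n is about 154 per arm and power is 92%, 77% and 88%, a material shortfall only at effect size 0.40. On the inclusive reading the stated figures stand, with an unexplained 5.3% allowance for loss after starting treatment.

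The weightier part is the analysis. An unadjusted t test on available month-3 forms is exposed to loss that may differ by arm. The planned month-3 change-from-baseline t test needs the same month-3 form, so it does not remove the exposure. The size and direction of any bias cannot be taken from the documents. These are secondary endpoints, and nothing here affects the PFS or OS tests.

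**What to change.** 1. In Section 9.6.1, base n on treated patients and restate it as 154 per arm with power 92% (HRQL), 77% (0.40) and 88% (0.45), unless the plan states that the 10% includes non-starters. In that case, say so and justify the implied 5.3% loss among treated patients.
2. Make the mixed model of Section 9.6.2 the primary month-3 estimate, adjusted for the baseline score and using all scheduled PRO forms at their actual times, including end-of-treatment forms. It is described there for HRQL, with the baseline score not named as a covariate; name it, and write the same model for the symptom scores. State that the estimate relies on data missing at random given the observed scores.
3. Keep the month-3 t test as a sensitivity analysis.
4. Report month-3 form completion by arm, with reasons for missing forms.

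Do not substitute the end-of-treatment form for the month-3 value in the primary test: it mixes assessments from different weeks and changes the question. At most, use it in a sensitivity analysis.

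The cost is SAP wording and a slightly lower stated power. The forms are already scheduled.
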